6.2 Secondary Outcome

Tumor Response measured as:

- I) Tumor size (mm) and clearance (yes or no) will be evaluated clinically and using non-invasive D-OCT, HIFU and RCM imaging at baseline, Day 30 and Month 3 (Section 5, Appendix 1). If residual tumor is identified at 3 months follow-up, patients will receive conventional treatment according to national guidelines. Imaging techniques are described in section 6.3.
- II) Histological verification of tumor clearance will be performed 3 months after first treatment using tissue sections from a 4 mm punch biopsy. If residual tumor is identified at 3 months follow-up, patients will receive conventional treatment according to national guidelines.

6.3 Methods for Outcome Assessment

6.3.1 Clinical Evaluation and Digital Photography

Clinical evaluation of LSRs (erythema, edema, flaking, crusting/scabbing and pustulation) in treated areas will be performed by a non-blinded physician using a FDA-approved LSR scale at Days 1, 5, 14 and 30 after baseline. The scale assesses severity of individual LSR parameters on a 0-4 points scale: none, mild, moderate, severe. Tumor size (mm) and clearance (yes or no) will also be evaluated by standard clinical dermoscopy at Day 30 and Month 3 (Appendix 1). Digital photography using a Canon Camera will be performed prior to, during, after treatment, and at control visits under standardized conditions. All images are assigned an ID-number and anonymized.

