3.4 Summary of Outcome Measures and Methods

Outcome measures and methods/techniques are summarized below. Detailed descriptions are presented in Section 6 and Table 1 (Appendix 1).

Primary outcome:

To investigate tolerability of topical AFL-assisted cisplatin+5-FU therapy for BCC by evaluating:

- I. Severity and duration of clinical local skin reactions including erythema, edema, scabbing, flaking and pustulation assessed by a physician using an established 0-4 point scale (none, mild, moderate, severe) from 0-30 days post-treatment.

- II. Occurrence of side effects (prolonged erythema/edema, hyper/hypopigmentation, scarring and infection) up to 3 months post-treatment.

Secondary outcome:

- 1) To monitor BCC tumor size and clearance based on clinical assessments and dermoscopy, supported by non-invasive imaging techniques including dynamic optical coherence tomography (D-OCT), reflectance confocal microscopy (RCM), high intensity focused ultrasound (HIFU) and histological analysis up to 3 months post-treatment.

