3.5 Preliminary Study

In the beginning of the trial period, a preliminary study in 4-6 patients of the intended treatment will be conducted to confirm: a) uniform cisplatin and 5-FU uptake in treated BCC tumors and b) no clinically relevant systemic drug uptake. Thus, up to 6 patients will each provide a single 4 mm punch biopsy of a treated BCC and one 5 ml blood sample, both taken 24 hrs after AFL-assisted cisplatin+5-FU. Drug biodistribution imaging of tumor sections and drug quantification in blood will be performed at Copenhagen University using well-established analytical techniques. A biobank and contracts of collaboration pertaining to the exchange of anonymized data between institutions will be devised.

4. Participants

Up to 12 patients with superficial BCC and 12 patients with nodular BCC will be evaluated following AFL-assisted cisplatin+5-FU treatment. The unspecific inclusion of “up to” 12 patients reflects the explorative nature of this tolerability study. Should fewer patients per group provide adequate data on LRSs associated with the treatment (for example if all patients demonstrate severe LSRs), the inclusion of 12 patients will not be performed in order to spare them potential discomfort.

Recruitment will be performed by physicians at the dermatological department, Bispebjerg Hospital and by private practice dermatologists in the Copenhagen area. Procedures for informed consent are included in Bilag 2-4.

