5.2.4 Topical 5-Fluorouracil (5-FU)

After cisplatin removal, the well bandage is disposed of and a thick amount of Efudix® 5% 5-FU cream (Meda Pharmaceuticals A/S, UK) is applied to the entire test area (corresponding to up to 0.125 ml per cm² skin). After 5-FU application, transparent dermatological film (TegaDerm® film dressing, 3M Medical, MN, USA) is applied to the test area as an occlusive dressing. The cream is left on the skin until next control visit. Thus, on Day 1 and 5, Efudix cream is reapplied at the same dose. The cream is removed on Day 7 after AFL treatment.

STUDY SET UP	Visit 1 Screening	Visit 2 Treatment Day 0	Visit 3 Day 1	Visit 4 Day 5 +/- 2 days	Visit 5 Day 14 +/- 3 days	Visit 6 Treatment* Day 30 +/- 5 days	Visit 7 Month 3 +/- 5 days
Screening & enrolment							
Informed consent	✓						
Inclusion/exclusion criteria	✓						
Relevant medical history	✓						
Location of BCC	✓						
Pregnancy test when relevant		✓				✓	
Interventions							
AFL		✓				(✓)	
Apply topical cisplatin(60min)		✓				(✓)	
Apply 5-FU under occlusion		✓	✓	✓		(✓)	
Clinical LSR evaluation							
FDA-approved LSR scale		✓	✓	✓	✓	✓	
Clinical photos		✓	✓	✓	✓	✓	
Safety							
Clinical evaluation		✓	✓	✓	✓	✓	
Tumor size and clearance evaluation							
Clinical/dermoscopic photos		✓	✓	✓	✓	✓	
D-OCT		✓				(✓)	
RCM		✓					
HIFU		✓				(✓)	
Biopsy							✓

*Offered if BCC residual or recurrence; (✓): Treatment/technique can be relevantly applied if tumor residuals are identified clinically or by D-OCT/RCM and there is no crusting etc. LSR: Local skin reactions, RCM: Reflectance confocal microscopy, D-OCT: Dynamic optical coherence tomography

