6.1 Primary Outcome

Tolerability measured as:

I) Local Skin Reactions (LSRs)

Non-blinded, clinical evaluation of erythema, edema, flaking, crusting/scabbing and pustulation in treated areas will be performed by a physician using a FDA-approved 0-4 point LSR scale at Days 1, 5, 14 and 30 after AFL exposure (Appendix 1). Standardized,

clinical photographs are taken to document LSRs at each visit.

II) Side Effects

Non-blinded, clinical evaluation of prolonged erythema or edema, hyper- or hypopigmentation, scarring and infection will be evaluated up to 3 months after initial AFL treatment.

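### The graded skin reactions named for the primary outcome omit erosion/ulceration and blistering, which the protocol itself expects, and the 0-4 scale has five scores but four labels

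*Combined protocol and SAP*

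**What the plan says.** Part I of the primary outcome in Section 3.4 is "Severity and duration of clinical local skin reactions including erythema, edema, scabbing, flaking and pustulation", scored "using an established 0-4 point scale (none, mild, moderate, severe) from 0-30 days post-treatment". Section 6.1 specifies "clinical evaluation of erythema, edema, flaking, crusting/scabbing and pustulation in treated areas", "using a FDA-approved 0-4 point LSR scale at Days 1, 5, 14 and 30 after AFL exposure". Section 6.3.1 repeats the list: "Clinical evaluation of LSRs (erythema, edema, flaking, crusting/scabbing and pustulation) in treated areas will be performed by a non-blinded physician". Part II in Section 3.4 is "Occurrence of side effects (prolonged erythema/edema, hyper/hypopigmentation, scarring and infection) up to 3 months post-treatment".

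Appendix 1 names the scale but prints neither its items nor its grade anchors.

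Section 7.2 expects a sequence of inflammation, necrosis with skin erosion, and healing. It puts the incidence of erosion at 50-95% and warns of blistering and ulceration without giving rates. Section 11 names erosion/ulceration among the anticipated reactions.

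Sections 8.1 and 8.2 treat an expected treatment-related reaction as an AR, recorded with dates and severity. Reactions on the LSR scale are kept out of AE entries in the CRF, even when they need treatment. Section 8.3 requires every SAE to be reported.

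**The concern.** Tolerability is the primary outcome, and its graded part rests on the LSR scores, which are also what Section 9.3 proposes to summarise and test. Section 7.2 describes a three-stage reaction. The middle stage is defined by erosion, and no named item grades it. A patient with marked erosion but modest erythema, edema, flaking, crusting and pustulation would score low on part I.

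The label gap adds to this. If the documents do not fix which number means severe, two assessors can give different scores to the same skin, and a reader cannot tell what a median score of 3 means.

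The reporting boundary is also incomplete. Section 8.2 keeps scale LSRs out of AE entries, and Section 8.1 defines an SAE as a kind of adverse event. The documents do not say outright that a serious LSR goes through 8.3.

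**Working it through.** The plan gives no figure to reproduce here: Section 9.1 says that no formal sample size calculation was made. The check compares lists, with simple arithmetic for scale.

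**Step 1: reactions expected against reactions named.**

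| Reaction | Expected in 7.2 or 11 | Graded item in 6.1 and 6.3.1 | Part II side effect |
|---|---|---|---|
| Erythema | yes | yes | only if prolonged |
| Edema | yes | yes | only if prolonged |
| Scabbing/crusting | yes | yes | no |
| Flaking | yes (11) | yes | no |
| Erosion | yes, 50-95% | no | no |
| Ulceration | yes, no rate | no | no |
| Blistering | possible, no rate | no | no |

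Pustulation is the fifth graded item. Section 7.2 lists scabbing and erosion on separate lines, and Section 11 names crusting apart from erosion/ulceration, so the crusting item cannot simply be read as covering erosion.

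**Step 2: how many patients.** The inputs are 24 planned patients, 12 per subtype (Section 9.1), and erosion at 50-95% (Section 7.2). Expected count = n × p.

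- All patients: 24 × 0.50 = 12.0; 24 × 0.95 = 22.8.
- Per subtype: 12 × 0.50 = 6.0; 12 × 0.95 = 11.4.

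The 24 is a planned number. Section 4 allows fewer, and Section 4.4 replaces patients who withdraw, so the number treated can also be higher.

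**Step 3: what the AR route records.** Under Section 8.2 an AR has start and end dates, so duration is available. Its severity is graded by transience and effect on daily activities. An erosion that heals and does not disturb daily life could be a mild AR whatever it looked like. What is missing is a local severity grade at each LSR visit, comparable with the other five items.

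**Step 4: scores and labels.** The integers 0, 1, 2, 3, 4 are five scores. None, mild, moderate and severe are four labels. Taking none as 0, severe is 3 if score 4 is the unlabelled one, and 4 if the gap is at 1, 2 or 3. The documents do not say which.

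**The case against.** The strongest reply is that the scale already exists and is not printed. Section 3.4 introduces the items as examples, so the form may already include erosion or blistering. That stands as a limit. Sections 6.1 and 6.3.1, however, give the five items without any such opening, and Appendix 1 does not resolve it. Pustulation might be meant to cover some blistering, but no section says so.

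The second reply is that erosion would be captured anyway: as an AR with dates and severity, in the standardized photographs of Section 6.1, at the clinical safety evaluations in the schedule, and in the final report under Section 8.4. This also stands, and it reduces the point to the missing visit-by-visit grade. The trial is uncontrolled and exploratory, which reduces it further.

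A reader might infer more than the documents support:

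- *That erosion goes unrecorded.* The AR route contradicts this.
- *That the label gap disturbs a stopping threshold.* Section 4 mentions severe reactions only as an illustration ("for example if all patients demonstrate severe LSRs") and sets no score.
- *That the Day 0 entry for the "FDA-approved LSR scale" in the study set-up table contradicts Sections 6.1 and 6.3.1.* Section 3.4 covers days 0-30, and the other two sections list the visits after exposure, so a Day 0 score plus four follow-up scores is a natural reading.
- *That 24 caps the number treated.* Replacement of withdrawals means it does not.

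**Conclusion.** The point holds at moderate size. Followed as written, Sections 6.1 and 6.3.1 give no LSR grade to erosion/ulceration or blistering, although the protocol expects erosion in at least half of patients (about 12 to 23 of the planned 24). The severity component of the primary outcome may therefore understate the local reaction.

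The amount cannot be computed, because the documents give no severity for erosion and no rate for ulceration or blistering. The counts assume that the Section 7.2 range is a per-patient incidence that applies to this regimen. The conclusion assumes that the graded items are the five named; if the form already holds the others, the defect is only that the protocol does not list them.

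The mismatch of five scores and four labels is a definite text defect on any reading. The handling of a serious LSR needs a clarifying sentence. Section 8.3 is already unqualified, so this is not evidence that such events would go unreported.

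**What to change.** 1. Add erosion/ulceration and blistering to the graded items in Sections 6.1 and 6.3.1, at the visits where the LSR scale is already used. If the established scale holds them, list them. If not, grade them as supplementary items with stated anchors and report them separately, leaving the established scale unaltered.
2. Print the scale's items in Appendix 1 with one anchor for each score. Give five labels for 0-4, or restate the range as 0-3 if that is what the form uses.
3. State in Section 8.2 that an LSR meeting a seriousness criterion is also reported under Section 8.3.

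Steps 2 and 3 cost only text. Step 1 costs at most two CRF rows per visit: 2 × 4 = 8 more grades per patient over Days 1, 5, 14 and 30, or 2 × 5 = 10 if Day 0 is also scored. It needs no new visit or procedure. The downsides are some double recording with ARs, a reported reaction burden that may look higher, and supplementary grades that cannot be compared with other uses of the scale.

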6.3.2 Imaging

All imaging devices have the size of a modern ultrasonography system and handheld, flexible probe. All systems are CE-marked and FDA approved.

High Intensity Focused Ultrasound (HIFU)

HIFU will be performed at baseline, day 30 (if imaging is not obstructed by overlying skin reactions) and month 3 after treatment. A GE LOGIQ P9 unit (General Electric Medical Systems, known as GE Healthcare, Little Chalfont, Buckinghamshire, UK) with a high frequency probe 9 - 15 MHz will be used to identify tumors in skin. The system is CE marked to council directive 93/42/EEC on medical devices (FDA K152309) with a 50-200 μm resolution and a penetration depth of 0.75-2 cm. HIFU allows volumetric images of tumors in real-time, using 4D transducers. BCC tumors are characterized as well-defined, black, round to elongated areas often with distinct internal white dots. The HIFU modality is sensitive to the generally slower blood flow in skin. During imaging, standard imaging gel is placed on the skin in order to avoid skin compression under examination. The acquired images are saved in a digital archiving computer system for subsequent evaluation.

Dynamic Optical Coherence Tomography (D-OCT)

D-OCT will be applied at baseline to delineate horizontal and vertical BCC tumor margins and subsequently customize settings for relevant AFL channel dimensions. D-OCT will also be used to assess tumor size and clearance at control visits on Day 30 (if imaging is not obstructed by overlying skin reactions) and Month 3 after treatment (Section 5, Appendix 1). A commercially available, CE-marked (CE 545451, FDA K153283) OCT system (Vivosight[®] DX, Michelson Diagnostics Ltd., Kent, UK) with a laser wavelength of 1305 nm will be used.

OCT works similarly to ultrasound: instead of acoustical waves, the reflection of infrared light emitted from the skin is measured, and the signal strength is imaged as a function of position. The applied OCT system has a 5–7.5 μm resolution and a penetration depth of 1–2 mm. In this study, a multi-slice modality consisting of 250 B-scans will be used. The OCT skin images are presented in both cross-sectional and *en face* mode. BCCs appear as well-defined, dark, round to elongated islands with clefting, arborizing vessels and increased blood flow. Images which visualize microcirculation in the skin are acquired using the dynamic OCT-signals (D-OCT) also termed “speckle variance” using the Vivosight system and relies on the higher variation of speckles caused by motion i.e. blood cells. The D-OCT data is collected concurrently with structural OCT data, and

displayed as a red overlay on the conventional OCT images. D-OCT images can be analysed and vessel flow calculated using an integrated software tool (Michelson diagnostics Ltd. Kent, UK). Flow is represented by an arbitrary number since D-OCT does not measure flow in m/s.

Reflectance Confocal Microscopy (RCM):

In vivo RCM is an advanced bedside microscope that can be attached to the skin. It offers visualization of epidermis and upper dermis at almost histological resolution. In this study, a commercially available CE-marked (CE 0459, FDA K080788) confocal microscope (VivaScope Multilaser 1500°, Caliber ID Inc., Rochester, NY, USA) in 785 nm mode is used. Horizontal tumor margins are confirmed at baseline and Month 3 after treatment (Section 5, Appendix 1). RCM provides horizontal sections of the skin with a penetration depth of 200–300 µm and a lateral resolution of 0.5 µm. VivaBlocks° will be acquired from each test area in 3 depths: between 30–40µm, at dermo-epidermal junction (80-110 µm), and between 150–200 µm. Subsequently, series of image stacks, “VivaStacks”, will be obtained from skin surface to papillary dermis. BCCs are indentified as having palisading bright cells in characteristic BCC islands with clefting, inflammation and dilated vessels. RCM has previously been used to non-invasively identify BCC lesions and monitor topical 5-FU treatment (12-15).

Imaging Software and Analysis

For the evaluation of D-OCT, RCM and HIFU images, qualitative and quantitative measurements will be obtained. Skin morphology in D-OCT and RCM images is evaluated using the integrated VivoSight° software for the OCT and the integrated VivaScan° software for the RCM VivaScope°. Furthermore, OCT, RCM and HIFU images will be analyzed using ImageJ software (Java-based freeware, National Institutes of Health, Maryland, USA).

6.3.3 Histology

At the 3 month visit, a 4 mm punch biopsy will be taken centrally in treatment area for histological verification of tumor clearance. Biopsy tissue will undergo standard sectioning and histological evaluation by a board-certified pathologist at the Department of Pathology, Bispebjerg Hospital. If tumor residual/recurrence is confirmed, test areas will be treated according to clinical guidelines.

7. Potential Risks and Side Effects

In general, no serious or systemic side effects are assumed but will be reported to the relevant authorities if they occur. Topical 5-FU cream and AFL are used daily at Bispebjerg Hospital's dermatological clinic and are well-tolerated. Cisplatin has previously been examined in a live pig study where no systemic drug uptake or effects were observed. Any obtained information about adverse effects related to this study will be recorded systematically.

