4.2 Exclusion criteria

Subjects meeting any of the following criteria are not eligible to participate in this study:

1. High-risk BCC
 - i. Tumors in the following anatomical locations: midface, orbital, ears
 - ii. Size: >20 mm in facial/scalp areas or > 50 mm in non-facial/non-scalp areas
 - iii. Subtype: morpheaform and micronodular BCC
 - iv. History: Gorlin syndrome or immunosuppression
2. Previous treatment of the BCC lesion
3. Known allergy to cisplatin or Efudix®
4. Other skin diseases present in the treatment area
5. Tattoo in the treatment area which may interfere with or confound evaluation of the study
6. History of keloids which is deemed clinically relevant in the opinion of the investigator
7. Fitzpatrick skin phototype IV-VI
8. Lactating or pregnant women

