5.1 Treatment Procedure

5.2.1 Treatment Area Demarcation

At baseline (Day 0), BCC delineation will be performed clinically and by D-OCT, RCM and HIFU imaging. The treatment area will include the delineated tumor and a 5 mm margin of surrounding skin. After delineation, treatment areas will be photographed and mapped on a transparent template to document baseline tumor size and location.

5.2.2 Ablative Fractional Laser (AFL):

Before AFL exposure, hairs will be shaved and treatment areas numbed with standard local analgesia (lidocaine HCL 1% +epinephrine 1:100.000 injection). Depending on tumor thickness, treatment areas will then be exposed to 1-2 stacked pulses of maximum 50 mJ/microbeam (mb) and up to 10 % density. Specific laser settings are established based on results from a currently ongoing clinical trial at Bispebjerg Hospital (EudraCT-nr 2017-002843-14).

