7.4 Punch Biopsy and Blood Sampling

Prior to 4 mm biopsy local analgesic will be used to reduce pain. The biopsy may leave a punctiform scar. Needle-pricks associated with injection and blood sampling (preliminary study) are associated with discomfort. The risk of infection is low (<1%), and will be managed with antibiotics provided by the investigator.

8. Safety Considerations

Patients are followed closely in the initial 30 days after treatment and particularly in the first 14 days. Complete tumor removal is ensured through histological analysis at Month 3. In the event of inadequate treatment response at 3 months, or in the event of withdrawal, patients will receive conventional BCC treatment and follow-up according to national guidelines.

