10.4 Biobank

In the preliminary study, one 4 mm punch biopsy taken from the treated skin area and one 5ml blood sample per patient will confirm adequate local drug uptake and limited systemic permeation. Biopsies and blood samples are sent for analysis by collaborators at Copenhagen University. No extra material will be taken. Any remaining biological material will be returned to primary investigator [name], Bispebjerg Hospital at the end of the study for potential use in future investigations. The material will be handled confidentially and will not be used in other scientific studies without Videnskabsetisk Komite's permission. Prior to storage, permission will be sought from Datatilsynet as well as patients. The biobank expires September 1, 2019 whereafter the material is kept for 10 years for future research and thereafter be destroyed.

11. Ethics

No previous trials have investigated AFL-assisted cisplatin+5-FU as a topical treatment in patients. Based on our preclinical results, we expect to successfully treat study participant's BCCs. During the trial, individual participants will be followed closely by treating phycisians. In the event of side

effects, these will be managed according to guidelines by investigating physicians. In the event of an unsuccessful treatment outcome, histological assessment should detect residual tumor tissue at 3 months control—a duration which is in accordance with general guidelines for established non-surgical BCC treatments. Patients will receive conventional therapy to ensure complete tumor removal. Beyond removal of the tumor, patients are not anticipated to benefit from the study.

While cisplatin and 5-FU are chemotherapeutics, side effect profiles associated with IV therapy (i.v. doses: 100 mg/m² (cisplatin); 400-600 mg/m² (5-FU)) cannot be transferred to the topical administration route used here. We do not anticipate systemic drug exposure due to the applied ultralow drug doses and small treatment surface areas. On the other hand, notable local erythema/edema, flaking/scaling, crusting, and erosion/ulceration are anticipated and represent, in addition to the inconvenience of multiple visits to the Hospital as well as invasive biological sampling, drawbacks of study participation. Still, as with standard 4 week topical 5-FU treatment, we expect local skin reactions to be tolerable and heal without sequelae.

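### One central 4 mm punch shows only that the sampled tissue is free of tumor; it cannot support the Section 8 statement that complete removal is ensured, and should not be reported as lesion clearance

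*Combined protocol and SAP*

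**What the plan says.** Section 6.2 II defines the histological part of the secondary outcome: "Histological verification of tumor clearance will be performed 3 months after first treatment using tissue sections from a 4 mm punch biopsy". Section 6.3.3 fixes the site: "a 4 mm punch biopsy will be taken centrally in treatment area for histological verification of tumor clearance". Neither section describes a second or peripheral punch.

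Section 4.2 sets the upper size limits by excluding "Size: >20 mm in facial/scalp areas or > 50 mm in non-facial/non-scalp areas". Section 5.2.1 adds a 5 mm margin around the tumor to form the treatment area, and has that area "mapped on a transparent template to document baseline tumor size and location".

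Section 8 draws the safety conclusion: "Complete tumor removal is ensured through histological analysis at Month 3". Section 11 is milder: "histological assessment should detect residual tumor tissue at 3 months control".

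Histology is not the only method. Section 3.4 (Summary of Outcome Measures and Methods) has tumor size and clearance judged "based on clinical assessments and dermoscopy, supported by non-invasive imaging techniques", with histology also in support. Sections 6.2 I, 6.3.1 and 6.3.2 place clinical, dermoscopic, D-OCT, ultrasound and RCM assessment at Month 3. Under Section 6.2, residual tumor found at that visit leads to conventional treatment.

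**The concern.** A negative punch is evidence about the tissue removed. Calling it verified clearance of the lesion assumes that any remaining tumor would lie in the central 4 mm. Nothing in the protocol supports that assumption for larger lesions.

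The error runs one way: a lesion with off-centre residual tumor is counted as histologically clear. With 12 lesions per subtype, each such miss adds 1/12 = 8.3 percentage points to that subtype's rate. Clearance is a secondary outcome, but Section 9.1 weighs adverse events against observed efficacy and treats the 24 lesions as enough to estimate benefit and risk. An inflated rate would therefore feed into the trial's own conclusion.

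The Section 8 sentence also credits histology alone with guaranteeing removal. That hides the risk that remains, namely residual tumor missed by every method at Month 3, the last study visit.

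**Working it through.** The protocol gives no biopsy sensitivity, expected clearance rate or sample-size calculation, so there is no planned figure to reproduce. The check is geometric.

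**Inputs from the protocol.** Punch diameter 4 mm, so radius 2 mm, taken centrally (6.3.3). Tumor diameter d up to 20 mm or 50 mm (4.2). The margin is 5 mm all round (5.2.1), so the centre of the treatment area is taken as the centre of the tumor.

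**Assumptions, for illustration only.** Tumors are circular. There is one circular residual focus of radius f, lying wholly inside the original tumor. Touching the punch counts as detection. True clearance is 75% (3 of 12 lesions with residual tumor).

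**Step 1: share of tumor surface sampled** = (4/d)², capped at 1.
- 5 mm: 16/25 = 64%
- 10 mm: 16/100 = 16%
- 20 mm: 16/400 = 4%
- 50 mm: 16/2500 = 0.64% (the extreme case)

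Full coverage occurs only at 4 mm or less.

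**Step 2: chance that the punch touches the focus.** Let R = d/2. Contact occurs if the focus centre lies within c = 2 + f of the tumor centre. The focus centre can lie at most A = R − f from it.
- Anywhere: (c/A)²
- Inner half (centre within R/2): (c/(R/2))²
- Outer half (centre between R/2 and A): (c² − R²/4)/(A² − R²/4)

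Each is bounded between 0 and 1. For a 2 mm focus (f = 1, c = 3):
- d = 5: A = 1.5, below c, so contact is certain.
- d = 10: A = 4. Anywhere 9/16 = 56%; inner half 100%; outer half (9 − 6.25)/(16 − 6.25) = 28%.
- d = 20: A = 9. Anywhere 9/81 = 11%; inner half 9/25 = 36%; outer half 0%, because c = 3 is below R/2 = 5.

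**Step 3: expected punch-based clearance** = 1 − 0.25 × P(contact), from inner-half to outer-half placement.

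| Tumor | Focus | P inner half | P outer half | Punch-based clearance (true 75%) |
|---|---|---|---|---|
| 5 mm | 2 mm | 100% | 100% | 75% |
| 10 mm | 1 mm | 100% | 0% | 75-100% |
| 10 mm | 2 mm | 100% | 28% | 75-93% |
| 10 mm | 4 mm | 100% | 100% | 75% |
| 20 mm | 1 mm | 25% | 0% | 94-100% |
| 20 mm | 2 mm | 36% | 0% | 91-100% |
| 20 mm | 4 mm | 64% | 0% | 84-100% |

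With the 2 mm focus placed anywhere, the rate is 1 − 0.25 × 0.5625 = 86% at 10 mm and 1 − 0.25 × 0.111 = 97% at 20 mm.

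The model is two-dimensional and ignores depth. Touching the punch does not guarantee that standard sections show tumor, which would make detection worse. Several residual foci would make it better.

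**The case against.** The strongest reply is that the plan does not lean on the punch. Section 3.4 puts clinical assessment and dermoscopy first, 6.2 lists histology as a separate item, and imaging is repeated at Month 3. Residual tumor found by these means leads to treatment. This stands, and it is why the point is limited. A reader might infer that the trial's overall clearance result is invalid, or that patients with off-centre residual tumor go unrecognised. The documents do not support either: only the histological rate rests on the punch. The reply does not rescue Section 8, which credits histology alone.

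A second reply is that the size limits are ceilings and typical lesions may be small. That also stands: near 5 mm, or with central residual tumor, the model shows no bias. Section 11 does mention "small treatment surface areas", but in arguing about systemic exposure, and it gives no diameter.

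Three further readings are tempting but go too far:
- The bias at 10 mm might be put higher by letting the focus extend beyond the original tumor. Residual tumor should be modelled inside it; a 4 mm focus in a 10 mm tumor then shows no bias.
- One might ask for the punch to be aimed at the most suspicious site. That is a trade-off, not a correction: it ends uniform sampling in groups of at most 12 and makes histology depend on the methods it is meant to support.
- Residual tumor is 'identified' in 6.2 and 'confirmed' in 6.3.3. This is not a contradiction, since both lead to treatment. The Section 11 wording is already hedged.

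**Conclusion.** The concern holds in a limited form. One central 4 mm punch cannot ensure complete tumor removal, so the Section 8 statement is unsupported. The histological result is correctly described as absence of tumor in the sampled tissue. Misses can only raise the histological clearance rate.

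The sampled shares follow directly from the punch size for circular tumors. The clearance ranges depend on the assumed 75% true clearance, a single focus and its placement. They show that the bias could be nil at 5 mm and substantial at 20 mm, but they do not estimate it. Its true size cannot be computed from the documents.

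Severity is low to moderate: this is a supporting method for a secondary outcome of an exploratory, uncontrolled trial, and the primary tolerability outcome is untouched.

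**What to change.** 1. **Section 8:** replace the claim that removal is ensured. State that the biopsy samples only part of the treated area, and that the judgment of clearance also relies on the Month 3 clinical, dermoscopic and imaging assessment.
2. **Section 6.2 II:** report the result as 'no tumor in the central punch', not as lesion clearance, and present it by the baseline tumor size already recorded under 5.2.1.
3. **Reporting of clearance:** keep the clinical and dermoscopic lead of Section 3.4, show the punch result beside it, and list every lesion where the methods disagree.

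The cost is wording and one listing. No extra biopsy, scan or visit is needed. The price is that the histological result is stated less favourably.
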